3.0 SUBSTUDY DESIGN

A5361s is an optional substudy of REPRIEVE (A5332) and the Mechanistic Substudy of REPRIEVE (A5333s). Approximately 600 HIV-infected males and females who are enrolled in **REPRIEVE (A5332) with or without coenrollment into A5333s** will co-enroll in A5361s.

Participants will be followed for **up to 60** months from the date of enrollment into REPRIEVE (A5332) for the assessment of objective and self-reported measures of physical function. Based on their date of enrollment into REPRIEVE (A5332), participant follow-up on A5361s will be between **36** and **60** months.

Additional outcome measures and covariates to address the study objectives will be obtained from assessments performed as part of REPRIEVE (A5332) and A5333s (see [section 10.0](#) for more detail).

4.0 SELECTION AND ENROLLMENT OF PARTICIPANTS

4.1 Inclusion Criteria

4.1.1 Ambulatory participants co-enrolled in both REPRIEVE (A5332) and the Mechanistic Substudy (A5333s).

OR

Ambulatory participants that are newly enrolling into REPRIEVE (A5332) at A5333s ACTG sites.

4.2 Exclusion Criteria

4.2.1 Inability to ambulate independently (use of a cane or a walker is permitted) or rise from a chair without assistance.

4.3 Study Enrollment Procedures

4.3.1 Prior to implementation of this protocol, and any subsequent full version amendments, sites must have the protocol and the protocol consent form(s) approved, as appropriate, by their local institutional review board (IRB)/ethics committee (EC) and any other applicable regulatory entity (RE). Upon receiving final approval, sites will submit all required protocol registration documents to the DAIDS Protocol Registration Office (DAIDS PRO) at the Regulatory Support

Center (RSC). The DAIDS PRO will review the submitted protocol registration packet to ensure that all required documents have been received.

Site-specific informed consent forms (ICFs) WILL NOT be reviewed or approved by the DAIDS PRO, and sites will receive an Initial Registration Notification when the DAIDS PRO receives a complete registration packet. Receipt of an Initial Registration Notification indicates successful completion of the protocol registration process. Sites will not receive any additional notifications from the DAIDS PRO for the initial protocol registration. A copy of the Initial Registration Notification should be retained in their regulatory files.

Upon receiving final IRB/EC and any other applicable RE approvals for an amendment, sites should implement the amendment immediately. Sites are required to submit an amendment registration packet to the DAIDS PRO at the RSC. The DAIDS PRO will review the submitted protocol registration packet to ensure that all the required documents have been received. Site-specific ICFs WILL NOT be reviewed and approved by the DAIDS PRO, and sites will receive an Amendment Registration Notification when the DAIDS PRO receives a complete registration packet. Sites should retain a copy of the Amendment Registration Notification in their regulatory files.

For additional information on the protocol registration process and specific documents required for initial and amendment registrations, refer to the current version of the DAIDS Protocol Registration Manual.

Once a candidate for study entry has been identified, details will be carefully discussed with the participant. The participant will be asked to read and sign the approved protocol consent form.

For participants from whom a signed informed consent has been obtained, an ACTG Screening Checklist must be entered through the Data Management Center (DMC) Participant Enrollment System.

4.3.2 Protocol Activation

Prior to screening, sites must complete the Protocol Activation Checklist found on the ACTG Member website. This checklist must be approved prior to any screening of participants for enrollment.

4.3.3 Participant Registration

Participants who meet the enrollment criteria will be registered to the study according to standard ACTG DMC procedures. For participants from whom informed consent has been obtained, but who are deemed ineligible or who do not enroll into the protocol, an ACTG Screening Failure Results form must be completed and keyed into the database.

4.4 Co-enrollment Guidelines

Co-enrollment is allowed per REPRIEVE (A5332) guidelines.

5.0 STUDY TREATMENT

5.1 Regimens, Administration, and Duration

No drugs will be provided by this study. Pitavastatin/placebo will be provided per REPRIEVE (A5332) section 5.0.

Participants may enroll and continue participation in A5361s regardless of their status on REPRIEVE (A5332) study treatment.

5.2 Prohibited Medications

Per REPRIEVE (A5332).

6.0 CLINICAL AND LABORATORY EVALUATIONS

6.1 Schedule of Evaluations

All study visits for A5361s assessments should be timed to coincide with regularly scheduled REPRIEVE (A5332) or A5333s visits. The A5361s post-entry visits are scheduled in months after REPRIEVE (A5332) entry.

Evaluation	Entry (\pm 14 days) ¹	Post-Entry Evaluations (months) (Preferably completed at the REPRIEVE (A5332) or A5333s visit, however \pm 14 days of visit is acceptable) ²					
		0	Month 12	Month 24	Month 36	Month 48	Month 60 (see 6.2.1)
Modified Short Physical Performance Battery and Frailty Assessments	X	X	X	X	X	X	X
Rapid Eating and Activity Assessment for Patients Survey – Questions #26 and #27 only		X ³	X ⁴	X	X	X	X
Duke Activity Status Index⁵			X ⁴				

¹ Entry for participants newly enrolling into A5332 and A5333s or A5332 only, OR any subsequent follow-up visits for co-enrolled (A5332/A5333s) participants, up to month 24.

² Participants co-enrolled in A5332 and A5333s can enroll at any visit, up to month 24. The second visit will then be completed at the next A5332 or A5333s annual visit. Depending on the time of enrollment, participants will be followed from between 36 to approximately 60 months.

³ In the event that the A5361s entry visit coincides with the month 12 visit for A5332 or A5333s, REAP questions #26 and #27 will be completed as part of a combined A5361s entry and month 12 visit.

⁴ For newly enrolling A5332 participants at A5333s ACTG sites, REAP questions #26 and #27 at Months 12 and 24 and DASI at Month 24 will be captured as part of A5361s for participants not co-enrolled in A5333s.

⁵ At month 60, the DASI evaluation from the REPRIEVE (A5332) month 96 or study termination visit will be used.

6.2 Timing of Evaluations

6.2.1 Entry and Post-Entry Evaluations

For participants newly enrolling into REPRIEVE (A5332) and A5333s: **Enrollment into A5361s should preferably occur on the same day as enrollment into A5332 or A5333s** (within 14 days of the visit is acceptable), and **prior to initiation of randomized treatment in REPRIEVE (A5332)**.

For participants newly enrolling into REPRIEVE (A5332) only: Enrollment into A5361s should occur on the same day as enrollment into A5332 when possible (but must occur within 14 days of enrollment into A5332) and must occur prior to initiation of randomized treatment in REPRIEVE (A5332).

For participants already enrolled into **both** REPRIEVE (A5332) and A5333s: The A5361s entry visit can occur at any REPRIEVE (A5332) or A5333s visit (or \pm 14 days of the visit), up to the month 24 visit. Subsequent visits will follow the remaining schedule in [section 6.1](#).

For all participants: All post-entry visits should be scheduled to coincide with the q12 month regularly scheduled REPRIEVE (A5332) visits but within 14 days of visit is acceptable. Post-entry visits should be scheduled from the REPRIEVE (A5332) entry visit.

Enrollment completed in 2018 under PREPARE (A5361s) Version 1.0. In Version 2.0, an additional visit is added to occur at month 60. If the participant is past their Month 60 visit in the REPRIEVE (A5332) study, the PREPARE (A5361s) Month 60 evaluations can be performed at the next REPRIEVE (A5332) in-person visit. Refer to the A5361s Manual of Procedures (MOPS) for special instructions for participants who are already off-study.

ALTERNATE COMPLETION OF POST-ENTRY EVALUATIONS

- **If a participant can safely be seen for an in-person REPRIEVE (A5332) study visit, the A5361s visit that is due at the same time should also be completed.**

If local guidelines or restrictions prevent the site from completing any of the assessments (or components of the mSPPB or frailty assessments) required at a visit, the reason for the missing assessment should be documented in the source documents and on the corresponding CRF. Complete evaluations as possible, even if full mSPPB and frailty assessments cannot be performed.

- If a participant has an in-person REPRIEVE (A5332) study visit but A5361s assessments could not be completed due to local guidelines or restrictions, the assessments should be completed at the next REPRIEVE (A5332) in-person visit if the restrictions have been canceled by then.
- If an in-person REPRIEVE (A5332) study visit that coincides with an A5361s visit is delayed or missed, the A5361s visit should be completed whenever the participant is next seen for an in-person REPRIEVE (A5332) visit.

6.2.2 Discontinuation Evaluations

Premature Discontinuation from REPRIEVE Study Treatment

No additional A5361s assessments are required at the time of premature discontinuation from REPRIEVE (A5332) study treatment.

Participants who prematurely discontinue from REPRIEVE (A5332) study treatment will continue to be followed as indicated in [section 6.1](#).

Premature Discontinuation from REPRIEVE (A5332) Study

Participants who prematurely discontinue from REPRIEVE (A5332) will be discontinued from A5361s and have an A5361s discontinuation visit performed as indicated in [section 6.1](#).

Premature Discontinuation from Study A5361s

Participants who discontinue from A5361s will have an A5361s discontinuation visit performed as indicated in [section 6.1](#).

6.3 Instructions for Evaluations

All clinical and laboratory information required by this protocol is to be present in the source documents. Sites must refer to the Source Document Guidelines on the DAIDS website for information about what must be included in the source document:

<https://www.niaid.nih.gov/sites/default/files/score-source-documentation-requirements.pdf>.

If a participant is able to ambulate independently at entry but later is unable to complete the assessments, the participant should remain on study, and the reason for the lack of assessment should be recorded.

The protocol team and/or study monitoring entity (e.g., SMC) may determine that additional source data associated with procedures or evaluations performed per protocol should be entered into eCRFs so that the data can be used for analysis or to otherwise assist with interpretation of study findings. In such cases, sites will be officially instructed to enter the additional data into eCRFs from available source documentation.

6.3.1 modified Short Performance Battery (mSPPB)

6.3.1.1 Repeat Chair Stand

Repeat chair stand is a functional test of lower extremity performance that is highly affected by changes in muscle strength and has been proposed as a proxy measure of lower-extremity strength for the clinical setting. Participants rise from a standard height chair that does not have wheels or arms 10 times. Split times are captured after completion of both five rises and 10 rises (see MOPS for further details).

6.3.1.2 Grip Strength

Grip strength is an easily performed, inexpensive, reproducible assessment that is strongly associated with bone mineral density (BMD), fall risk, and fracture, and it is well correlated with more direct measures of lower-extremity strength. Three measurements with the dominant hand will be taken using a Jamar Dynamometer. (See MOPS for further details.)

6.3.1.3 Standing Balance Test

Participants are asked to stand in three different positions with progressive narrowing of the base of support, namely the side-by-side stand, the semi-tandem stand (i.e., heel of one foot touching the great toe of the other foot), the full tandem stand (i.e., heel-toe position), and the single-leg stand (i.e., opposite foot in hip-flexed, knee flexed position with toes 2 inches or more from the floor). The duration for which the participant can hold the stance without taking a step or grabbing for support is recorded. (See MOPS for further details.)

6.3.1.4 Gait Speed

Walking is a complex task requiring balance, mobility, strength, and coordination. In many functional performance batteries, including the mSPPB, timed walking is an integral component. It is an excellent predictor of lower extremity function and is well correlated with falls and fractures resulting from falls; it also is a strong predictor of disability and mortality. Two measurements of usual gait speed on a 4-meter course will be obtained. (See MOPS for further details.)

6.3.2 Frailty Self-Reported Components

These three questions inquire about an unintentional change in weight, whether the participant's health leads to limitations in vigorous activities, and whether the participant feels that "everything that I do is an effort."

6.3.3 REAP Questions #26 and #27

These questions will be administered at 12, 36, 48, **and 60** months, and **at** discontinuation as a measure of self-reported physical activity; these assessments are obtained at entry in REPRIEVE (A5332) and at month 24 in A5333s. In the event that **the A5361s entry visit coincides with the month 12 visit for A5332 or A5333s**, REAP questions #26 and #27 will be completed as part of a **combined A5361s entry and A5332/A5333s month 12 visit**.

For REPRIEVE (A5332) participants not enrolled in A5333s, REAP questions #26 and #27 at month 24 will also be completed as part of A5361s.

The questions are as follows: In an average week, how often do you: (usually/often, sometimes, rarely/never, does not apply):

- #26 Do less than 30 total minutes of physical activity 3 days a week or more? (Examples: walking briskly, gardening, golf, jogging, swimming, biking, dancing, etc.)
- #27 Watch more than 2 hours of television or videos a day?

6.3.4 DASI

In the event that enrollment is expanded to eligible A5332 participants at US ACTG sites, functional capacity (Duke Activity Status Index [DASI]) questionnaire will be completed at month 24 for participants not enrolled in A5333s.

For the month 60 evaluation, the DASI evaluation from the REPRIEVE (A5332) month 96 or study termination visit will be used.

7.0 ADVERSE EVENTS AND STUDY MONITORING

7.1 Definition of Adverse Events

An adverse event is any unfavorable and unintended sign (including an abnormal laboratory finding), symptom, or diagnosis that occurs in a study participant during the conduct of the study REGARDLESS of the attribution (i.e., relationship of event to medical treatment/study product/device or procedure/intervention). This includes any occurrence that is new in onset or aggravated in severity or frequency from the baseline condition.

7.2 Adverse Event Reporting Requirements in the Clinical Database

A5361s has no adverse event reporting requirements.

7.3 Expedited Adverse Event (EAE) Reporting to DAIDS

A5361s reporting of EAEs to DAIDS is not required because A5361s is an observational/non-interventional study (i.e., there are minimal interventional risks from the study for participants).

7.4 Study Monitoring

The Protocol Core Team will monitor the conduct and continued feasibility of the study via quarterly summaries of enrollment, study retention, co-enrollment, and endpoint evaluability. On an annual basis the Study team will prepare a Protocol Team Review Summary Letter for distribution to site investigators in accordance with the ACTG SOP for Study Data and Safety Monitoring.

The study status of PREPARE is monitored by the REPRIEVE DSMB as part of the REPRIEVE trial study monitoring plan.

Detailed plans for data monitoring will be outlined in a Study Monitoring Plan developed by the Statistical and Data Management Center (SDMC) prior to enrollment of the first participant.

8.0 CLINICAL MANAGEMENT ISSUES

Management of HIV antiretroviral therapies and complications of disease should be performed according to the REPRIEVE (A5332) protocol or routine clinical care, where applicable.

9.0 CRITERIA FOR DISCONTINUATION

- Request by the participant to withdraw.
- Request of the primary care provider if she or he thinks the study is no longer in the best interest of the participant.
- Premature discontinuation from REPRIEVE (A5332).
- At the discretion of the study monitor, site investigator, IRB, Office of Human Research Protections (OHRP), National Institute on Aging (NIA), NIAID, NHLBI, or other government agencies as part of their duties to ensure that research participants are protected.

10.0 STATISTICAL CONSIDERATIONS

10.1 General Design Issues

A5361s will determine the effects of pitavastatin on physical function and evaluate mechanistic pathways through which pitavastatin affects physical function.

The study will enroll participants from REPRIEVE (A5332) and its mechanistic substudy (A5333s) and follow them for **up to 60** months after entry to REPRIEVE (A5332). Treatment groups (placebo versus pitavastatin) will be defined according to randomization in REPRIEVE (A5332). The primary analyses for all treatment group comparisons will be intent to treat, while supportive secondary analyses as well as analyses examining mechanistic pathways will be as-treated.

While measures of physical function (including both objective and long-term measures of self-assessment) will be assessed as part of A5361s, many of the outcome measures of interest will be available through data collected in REPRIEVE (A5332) and A5333s, as outlined in the Table 10.1-1. If the target recruitment numbers cannot be achieved through A5333s enrollment, the study will open to all participants in REPRIEVE (A5332) enrolled at US ACTG sites. For these participants, only the outcomes measured as part of A5361s or REPRIEVE (A5332) will be available for analysis.

Table 10.1-1: Data Sources for A5361s Outcome Measures

Outcome Measure	REPRIEVE (A5332) Entry	Year 1	Year 2	Year 3	Year 4	Year 5
Physical function battery	A5361s ¹	A5361s ²	A5361s	A5361s	A5361s	A5361s
Frailty components	A5361s ¹	A5361s ²	A5361s	A5361s	A5361s	A5361s
Duke Activity Status Index (DASI)	A5332 ³		A5333s ⁴			A5332⁶
Self-reported physical activity and sedentary time (REAP) ⁵	A5332 ³	A5361s ²	A5333s ⁴	A5361s	A5361s	A5361s
Myalgia symptom assessment	A5332 ³	A5332 ³	A5332	A5332	A5332	A5332
Samples for inflammatory markers	A5332 ³	A5332 ³				
Fasting lipids and insulin sensitivity	A5332/ A5333s ³		A5332/ A5333s			A5332
CT scan for fatty infiltration of the skeletal trunk muscles	A5333s ³		A5333s			

¹ Will be available only to participants who enroll concurrently into REPRIEVE (A5332) and A5361s.

² Will be available only to participants who enroll into A5361s concurrently or within 12 months of REPRIEVE (A5332) entry.

³ For participants who enroll into A5361s after REPRIEVE (A5332) entry, the data and samples collected in REPRIEVE and A5333s prior to A5361s entry will be used.

⁴ In the event that enrollment is expanded to all A5332 participants, will be captured as part of A5361s for participants not enrolled in A5333s.

⁵ Questions 26 and 27 only.

⁶ **The DASI evaluation from the REPRIEVE (A5332) month 96 or study termination visit will be used.**

10.2 Outcome Measures

10.2.1 Primary Outcome Measures

10.2.1.1 Chair rise rate measured annually over **60** months

This primary outcome for the primary physical function objective is a simple transformation of the measured outcome of time to perform 10 chair stands. It is chosen to provide a continuous outcome for participants regardless of their ability to perform 10 chair stands.

It is a well-established measure of lower extremity strength and our previous studies in HIV-infected populations have shown that, among components of the SPPB, this measure is the most likely to show deficits [8,100]. In addition, in middle-age adults from the general population, chair rise rate is a strong independent predictor of mortality [123].

10.2.1.2 Inflammatory Index Score (IIS) quantified at 12 months

The IL-6 and TNF- α pathways are both hypothesized to lead to sarcopenia, muscle weakness, and decreased physical function. The IIS was found to be a better predictor than IL-6 or measures of TNF- α activity alone in a geriatric population [100] and is predictive of mortality in an HIV cohort [5]. This validated instrument will be used to address the effect of pitavastatin on systemic inflammation composed of serum IL-6 and sTNFR-1. The score is calculated with the following formula:

$$1/3 \log [\text{IL-6}] + 2/3 \log [\text{sTNFR-1}]$$

10.2.1.3 Paraspinal muscle density measured in Hounsfield units (HU) at REPRIEVE (A5332) entry and month 24.

10.2.2 Secondary Outcome Measures

10.2.2.1 Secondary physical function outcome measures assessed annually for **60** months.

Raw scores for each of the additional components of the SPPB (grip strength, gait speed, ability to hold the one leg stand for 30 seconds) as well as the composite SPPB score (composite scoring of chair stand, balance, and gait) measured annually to month **60**.

Physical function deficits defined as a composite SPPB score ≤ 10 assessed annually to month **60** [124,125].

Frailty (classified as non-frail, pre-frail, and frail) as well as the frequency of its components (exhaustion, weight loss, low activity, slow walk, grip strength) and the number of frailty components present [126].

Self-reported physical activity via two questions measured on a three-point ordinal scale on the REAP assessment.

10.2.2.2 Secondary outcome measures for the mechanistic objective quantified at REPRIEVE (A5332) entry and 12 months

Serum concentrations of each individual biomarker of the IIS (IL-6, sTNFR-1) as well as other biomarkers implicated in the pathogenesis of physical function impairment (these may include markers such as sTNFR-2, IP-10, IGF-1, TGF- β 1) or those that may mediate the effects of statin treatment on systemic inflammation (CMV IgG).

The specific list of biomarkers of interest may be modified closer to the time of analysis based on the identification of additional biomarkers or pathways involved in this process.

10.2.2.3 Secondary outcome measures for the mechanistic objectives related to fatty infiltration of the skeletal trunk muscles assessed at REPRIEVE (A5332) entry and 24 months:

Shoulder and upper back muscle density measured in HU.

Paraspinal and trunk muscle volume (area).

10.3 Randomization/Registration

Participants will be enrolled into A5361s via the ACTG enrollment system. See [section 4.0](#) for specific information on the timing of A5361s and REPRIEVE (A5332) enrollment.

10.4 Sample Size and Accrual

600 participants will be enrolled over a period of 2 years. Participants will be followed until the time of their 5-year assessment on REPRIEVE (A5332) (up to 60 months depending on the time of enrollment).

10.4.2 Sample Size Justification for Mechanistic Outcome Measures

With a sample size of 300 participants in each treatment group and conservatively assuming 10% of participants will be inevaluable for either REPRIEVE (A5332) entry or follow-up outcomes; we have 90% power to detect a 0.28 SD difference between the pitavastatin and placebo treatment groups for the systemic markers of inflammation and immune activation. For IIS, the magnitude of this change has been shown to be associated with a 10% increase in 10-year mortality risk [129].

For fat attenuation, with an estimated 20% drop-out or non-evaluable scans and standard deviation of 6 [130], we will have 95% power to detect a difference in paraspinal muscle density of 1.8 HU between the two groups. A difference of 1–3

HU is considered clinically significant and is the effect observed in exercise interventions [114,116-118].

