9.3 Analytic Methods

Pointwise treatment group comparisons will use linear regression adjusted for baseline to provide estimation of the difference in the baseline-adjusted level of the outcomes at the follow-up visit. Outcome transformations will be applied as appropriate. Treatment group comparisons of markers of inflammation and immune activation will be limited to those not described in A5333s. For the CT outcomes, the primary treatment comparisons are on all participants with the muscle function data (i.e. including those not enrolled into PREPARE). The analysis will also be conducted among the participants enrolled into PREPARE to ensure a consistent effect size. Unless a test for heterogeneity of effect (interaction between enrollment into PREPARE and treatment effect) suggests otherwise, the PREPARE cohort effect sizes will be presented to give content to the main findings, but inference will be made on the full cohort.

Analyses of CT outcomes will also assess the association of these changes with changes in lipid components and HOMA-IR as listed below. The linear regression for treatment group comparison described above will be expanded to evaluate each lipid component and HOMA-IR separately.

- Lipid components including LDL cholesterol and triglycerides
- HOMA-IR calculated as [glucose (mg/dL) x insulin (uIU/mL)]/ 405

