10.2 Analysis Data

The results for the primary physical function outcome, chair rise rate, will be used. Biomarker and CT outcome results from baseline and post-baseline (month 12 or month 24 for biomarkers and CT, respectively). The analyses using biomarker outcomes from A5333s and CT outcomes are limited to participants who were co-enrolled in A5333s.

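### The CT power in Protocol 10.4.2 rests on a sample that matches neither CT analysis set in the SAP, and 95% does not follow from its stated inputs

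*Protocol*

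**What the plan says.** Protocol 10.4.2 opens with the biomarker outcomes: "With a sample size of 300 participants in each treatment group and conservatively assuming 10% of participants will be inevaluable", and "we have 90% power to detect a 0.28 SD difference between the pitavastatin and placebo treatment groups". The next paragraph turns to fat attenuation. It allows 20% for drop-out or non-evaluable scans, takes an SD of 6, and states 95% power for 1.8 HU in paraspinal muscle density. It gives no other number of participants.

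Table 10.1-1 in Protocol 10.1 and the table in SAP 5 list A5333s as the only source of CT scans, at REPRIEVE entry and Year 2. The second limb of Protocol 4.1.1 admits "Ambulatory participants that are newly enrolling into REPRIEVE (A5332) at A5333s ACTG sites" without requiring A5333s. Protocol 10.1 describes opening the study to REPRIEVE participants outside A5333s and notes the consequence: "For these participants, only the outcomes measured as part of A5361s or REPRIEVE (A5332) will be available for analysis". SAP 3 lists participants not co-enrolling in A5333s as a recruitment pool, and SAP 7 plans baseline tables for those with and without scans.

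The SAP uses two CT sets. In SAP 9.3, "For the CT outcomes, the primary treatment comparisons are on all participants with the muscle function data", including those outside PREPARE; the PREPARE subset serves as a consistency check. For the pathway models, SAP 10.2 says that analyses using "CT outcomes are limited to participants who were co-enrolled in A5333s".

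**The concern.** Paraspinal muscle density is one of three primary outcomes, and the CT part of primary objective 1.2.2 rests on participants who have both chair-rise and CT data. The CT calculation treats every PREPARE participant as having a scan planned, although the eligibility rules allow some to have none. Its 20% deduction describes scans lost or unusable, not scans never scheduled.

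The SAP then moves the primary comparison to a cohort that reaches beyond PREPARE. The stated power therefore belongs to no set that will be analysed, and a reader weighing a null CT result against 95% power would be using the wrong yardstick. The protocol regards 1–3 HU as clinically significant, so changes in the detectable difference of a few tenths of a unit fall inside the range that matters.

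**Working it through.** **Inputs.** 300 per arm, 20% CT loss, SD 6 and 1.8 HU (Protocol 10.4.2); two-sided 5% (SAP 6.7). The share co-enrolled in A5333s, f, is not in the documents and is assumed below.

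**Formula.** Power = Φ(δ / (σ√(2/n)) − 1.960), with n evaluable per arm.

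**Check on the biomarker figure.** n = 300 × 0.9 = 270. 0.28 / √(2/270) = 3.253, and Φ(3.253 − 1.960) = 90.2%. The stated 90% reproduces. These samples come from A5332 (Table 10.1-1), so missing CT scans do not affect it.

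**The CT figure, with everyone scanned.** n = 300 × 0.8 = 240. The standard error is 6 × √(2/240) = 0.548, and 1.8 / 0.548 = 3.286. Power = Φ(3.286 − 1.960) = 90.8% (90.7% with the t distribution). The stated 95% does not reproduce.

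What would give a figure near 95%:
- One-sided 5% at 240 per arm: 95.0%. This conflicts with SAP 6.7.
- No loss, 300 per arm, two-sided: 95.7%. With 10% loss (270 per arm): about 94%. Both depart from the stated 20%.
- More participants: n = 2 × 6² × (1.960 + 1.645)² / 1.8² = 289 evaluable per arm, or 289 / 0.8 = 362 per arm before loss.
- Baseline adjustment: the residual SD must be 1.8 / (3.605 × √(2/240)) = 5.47. From 5.47 = 6√(1 − ρ²), ρ is about 0.41. The protocol states no correlation.

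**Co-enrollees only.** n = 300 × f × 0.8. The ρ columns replace SD 6 by 6√(1 − ρ²), which presumes that 6 is an unadjusted SD. Both f and ρ are assumptions.

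| f | n per arm | Power, unadjusted | Power, ρ = 0.5 | Power, ρ = 0.7 | Unadjusted difference detectable at 90% power |
|---|---|---|---|---|---|
| 100% | 240 | 91% | 97% | >99% | 1.78 HU |
| 80% | 192 | 83% | 92% | 98% | 1.99 HU |
| 60% | 144 | 72% | 84% | 95% | 2.29 HU |
| 50% | 120 | 64% | 77% | 90% | 2.51 HU |

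The unadjusted powers at f below 100% are t-based (83.4%, 71.8%, 63.9%; the normal formula gives 83.6%, 72.1%, 64.2%). The ρ columns use the normal formula. The last column is 3.2415 × 6 × √(2/n).

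**All A5333s participants.** The documents do not give the size of A5333s, so no power can be computed for the SAP 9.3 primary comparison.

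**The case against.** The strongest reply is that the low figures describe a supportive analysis. Under SAP 9.3, inference on CT rests on the full A5333s cohort unless a heterogeneity test suggests otherwise, and that cohort could exceed 240 evaluable per arm. This stands: a reader might infer that the primary CT comparison is underpowered, and the documents do not show that.

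A second reply is that the planned regression adjusts for baseline, which recovers power. This also stands in part. A moderate correlation would restore 95% at 240 per arm, but the protocol neither states one nor says whether its SD is already adjusted.

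Third, Protocol 10.1 presents wider enrolment as a fallback, and the synopsis wants a substantial proportion in A5333s. The eligibility rules permit participants without scans but do not require them. It would therefore go too far to say that the CT calculation describes a population the study does not enrol. No document says how many lack scans.

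Fourth, restating planning power changes no test and no data, and a null result will be read mainly from its confidence interval. That limits the consequence. It does not justify leaving a stated power for a primary outcome that fails to follow from its own inputs.

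**Conclusion.** The point holds for the CT paragraph only. Its implied 240 per arm corresponds to neither the A5333s cohort used for the primary comparison nor the co-enrolled subset. Its 95% is about 4 points above what its own inputs give at two-sided 5%, even in the best case for PREPARE of full co-enrolment.

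How far power among co-enrollees falls below that depends on two quantities the documents do not supply: the co-enrolled share and the baseline/follow-up correlation. Across the assumed values of 50–80% and 0–0.7, it runs from 64% to 98%. For the SAP 9.3 primary set, neither the direction nor the size of the error is known.

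Two further inferences are tempting but unsupported. Because the 300 per arm appears in the biomarker sentence, a reader might think the biomarker power is also wrong; it reproduces. A reader might also carry the HU figures over to the SAP 10 pathway models. There, chair rise rate is the dependent variable and CT measures are explanatory, so power for a between-arm HU difference does not describe those models. A smaller co-enrolled sample reduces their precision, but these figures do not measure by how much.

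**What to change.** Rewrite the CT paragraph of Protocol 10.4.2, or add the statement to SAP 9, giving power or a detectable difference at two-sided 5%, with the baseline-adjustment assumption and the nature of the SD stated, for:

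- (a) A5333s participants per arm with paired evaluable scans, for the SAP 9.3 primary comparison;
- (b) participants co-enrolled in PREPARE and A5333s, for the supportive between-arm comparison.

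For the SAP 10 pathway models, report the co-enrolled number only, without a detectable HU difference. Leave the biomarker calculation (300 per arm, 10% loss, 90% power) as it is.

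Protocol 6.2.1 says PREPARE enrolment finished in 2018, so the number co-enrolled should be available. The count of paired evaluable scans has to come from A5333s, because closed enrolment does not establish it. The change is to wording and needs no new participants or data. Its cost is that the stated CT power may become less favourable.
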